**Nasal Non-Invasive Neurally Adjusted Ventilatory Assistance for VLBW
infants with a history of RDS requiring mechanical ventilation:**

The NIV-NAVA study

PI: [name]
Faculty PIs: [name], MPH and [name]

Last IRB review/approval: 4/18/22
University of Iowa IRB #201208771

Introduction:

Neurally adjusted ventilatory assistance (NAVA) is a technology that has grown rapidly and is now being utilized in neonatology intensive care units in the United States and Europe. NAVA aims to improve on patient ventilator synchrony by measuring diaphragmatic activity via an esophageally placed electrical catheter. This mode of ventilation provides individualized breath to breath support independent of air leak (Brown & DiBlasi, 2011; Stewart, Jagelman, & Webster, 2011).

Acute and chronic complications associated with endotracheal injury have been extensively studied and increase with the number of failed attempts at extubation and the duration of intubation (Attar & Donn, 2002; Gomes Cordeiro, Fernandes, & Troster, 2004; Joshi, Mandavia, Stern, & Wiglesworth, 1972; Miller & Carlo, 2008). By applying NAVA technology to these patients complications can be potentially minimized or completely avoided. NAVA has demonstrated that it is effective in decreasing peak inspiratory pressure (PIP) (Bengtsson & Edberg, 2010) and can provide additional ventilatory assistance (Stein & Howard, 2011) possibly facilitating earlier extubation and avoidance of complications associated with endotracheal intubation.

One of the main advantages of NAVA ventilation is the ability to improve patient ventilatory synchrony. Use of the electrical activity of the diaphragm (Edi) to trigger ventilator breaths decreases asynchrony. Edi triggered breath delivery facilitates breath to breath adjustment dependent on the patients' respiratory effort. As the patient increases their effort, the ventilator increases support based on adjustable ventilator settings (Cammarota et al., 2011; Clement, Thurman, Holt, & Heulitt, 2011; Colombo et al., 2008; de la Oliva, Schuffelmann, Gomez-Zamora, Villar, & Kacmarek, 2012; Schmidt et al., 2012).

Many of the benefits of NAVA ventilation have yet to be extensively studied in the preterm infants, with most of the known data coming from invasive applications of this

technology and adult studies (Beck et al., 2009; Cammarota et al., 2011; Schmidt et al., 2012; Stein & Howard, 2011).

This prospective study will look at extubated very low birth weight (VLBW) infants who received surfactant and are stable on their current distending pressures via continuous positive airway pressure (CPAP) or nasal cannula. This is a cross over trial utilizing NAVA to demonstrate that it can improve ventilatory support determined by improved blood gas parameters.

Preliminary Data:

We have retrospectively studied NAVA technology using a noninvasive strategy to provide nasal ventilation. All very low birth weight infants (VLBW) (less than 1500 grams) with respiratory distress syndrome treated with surfactant in our NICU from July 2011 to August 2012 and ventilated with noninvasive nasal NAVA were eligible. The change in partial pressure of carbon dioxide (pCO₂) of VLBW infants who had increased NAVA support in response to a capillary blood gas were studied. The pre- and post-intervention pCO₂ differences were determined for n=24 patients and the differences ranged from a decrease of 16 mmHg to an increase of 5 mmHg with a median value of -3.5 mmHg. This decrease was found to be significant using the Wilcoxon signed-rank test (p<0.001).

Study Design:

Prospective cross-over of NIV NAVA compared to nasal CPAP or high flow nasal cannula respiratory support in VLBW infants with a history of RDS.

Study Population / Eligibility:

- Birth weight was less than 1500 grams with clinical history of respiratory distress syndrome treated with surfactant
- Chronological age greater than or equal to seven days.
- At least 48 hours post-extubation and medically stable as determined by the treating medical team
- On one of the follow modes of mechanical support receiving a distending pressure via nasal pharyngeal tube (NP) or nasal cannula: continuous positive airway pressure (CPAP), intermittent mechanical ventilation (IMV), or neutrally adjusted ventilatory assistance (NAVA).
- Infants may be on high flow nasal cannula if the flow is large enough to provide a positive end expiratory pressure (PEEP) of 6 as defined by $PEEP\ of\ 6 = 0.68 * weight\ (kg) + 0.92$ (Sreenan, Lemke, Hudson-Mason, & Osiovich, 2001)
- Infants will be required to have a capillary blood gas obtained via heel stick after placement of heel warmer within 24 hours of study entry that demonstrates a pH of less than 7.35 and/or a partial pressure of carbon dioxide (pCO₂) greater than 45 mmHg.

Exclusion criteria:

- Severe congenital abnormalities
- Grade III or IV intraventricular hemorrhage.

Enrollment:

Local neonatal intensive care unit census will be screened at a minimum of one time per week to determine if there are neonates who potentially meet the enrollment criteria

defined above. The patients' clinical course will be monitored and when the infant requires minimal ventilatory support the parent(s) of said infants will be approached. The study will be explained and consent will be sought. If consent is granted, the infant's medical course will be monitored and once the infant is extubated and stable for a minimum of 48 hours on one of the approved ventilatory modes the routinely obtained morning capillary blood gas will be monitored until the infant meets study entry criteria.

Study Protocol:

Baseline Data Collection:

Demographic data: Patient gestational age at delivery, admission weight, receipt of surfactant administered, age at extubation, time since extubation, current post menstrual age, previous nitric oxide therapy, current nitric oxide therapy, and current weight.

Baseline vitals and ventilation mode: Heart rate, blood pressure, FiO₂, oxygen saturations, transcutaneous partial pressure of carbon dioxide (TCO₂) and current mode of ventilation will be recorded four times in a one minute period and the values averaged to minimize normal variation. Intervention time will be manipulated to begin no later than one hour after the previous feeding, as to minimize interruption of feedings given the typical every 3 hour feeding schedule used in our NICU.

Safety

TCO₂ monitor will be attached to the infant by respiratory therapy staff and the device will be calibrated according to protocol (reference TCO₂ monitor manual). Carbon dioxide diffusion through the skin will be monitored continuously during the intervention (Bromley, 2008) to assess for periods of hypo or hypercarbia.

Edi Catheter placement: Edi catheter size will be selected according to infant's weight and length. It will be inserted according to manufacturer's guidelines and adjustments will be made to optimize positioning (Maquet Critical Care AB). At the time of study initiation and every thirty minutes thereafter TCO₂, heart rate (HR), respiratory rate (RR), minute ventilation, peak Edi, minimum Edi, and PIP will be recorded four times in a one minute period and the values averaged to minimize normal variation. Current NAVA settings, oxygen saturations, FiO₂, and blood pressure (BP) will also be recorded at these times.

Physician member of the research team will be present at bedside during the entire study intervention.

NAVA settings:

Infants will be maintained on previous level of PEEP or calculated PEEP, rounding up to whole numbers. Initial NAVA level will be determined by starting with an initial NAVA level of 0.5 microvolts/cm of H₂O. The NAVA level will then be adjusted either by increasing or decreasing NAVA level settings by 0.1 microvolts/cm of H₂O to generate a PIP that is a minimum of 8 cm of H₂O greater than the current PEEP. Apnea alarm will be set at 5 seconds, which will initiate the NAVA back up setting if no electrical activity is detected by the Edi catheter. Back up NAVA settings will be set with a PIP of 12 cm of H₂O greater than current PEEP, respiratory rate of 60 breaths per minute (RR) and inspiratory time of 0.5 seconds. Fraction of inspired oxygen (FiO₂) will be adjusted to keep infant's oxygen saturations within previously established clinical parameters.

Infants who are currently receiving respiratory support via NAVA at the time of the study will have their NAVA level increased by 50%, rounding up to the nearest 0.1

microvolts/cm of H₂O. The other NAVA settings will be adjusted as previously described.

Study Intervention Procedure and Data Collection:

At initiation of intervention, and at time 30, 60, 90, and 120 minutes, TCO₂, heart rate (HR), respiratory rate (RR), minute ventilation, peak Edi, minimum Edi, and PIP will be recorded four times in a one minute period and the values averaged to minimize normal variation. Current NAVA settings, oxygen saturations, FiO₂, and blood pressure (BP) will also be recorded. At 60 minutes of intervention if the TCO₂ average has not decreased by 5 mmHg from baseline or has risen, the current NAVA level will be increased by 50%, and the HR, RR, minute ventilation, peak Edi, minimum Edi, and PIP will be recorded as described above. At 90 minutes if the TCO₂ average has not decreased by 5 mmHg from baseline or has risen; the NAVA level will be increased by 50% from the current level and data collected as describe at 60 minute intervention. At the completion of the study (120 minutes or pCO₂ outside of established limits) the HR, RR, BP, minute ventilation, FiO₂, oxygen saturations, peak Edi, minimum Edi, and PIP will be recorded four times in a one minute period and the values average to minimize normal variation. A capillary blood gas will be obtained according to standard unit protocol with a warmed heel.

If at any time during the study the TCO₂ level is greater than 80 mmHg the nasal pharyngeal tube will be evaluated for patency and exchanged if needed. If TCO₂ levels to do not return to less than 80 mmHg the study will be terminated and management will be deferred to primary medical team. If the TCO₂ level is less than 35 mmHg the infant will exit the study early and heart rate, FiO₂, oxygen saturations, HR, RR, peak Edi, minimum Edi, and PIP will be recorded four times in a one minute period. The values

will be averaged to minimize normal variation. Blood pressure will also be measured. A capillary blood gas will be obtained according to standard unit protocol with a warmed heel.

Statistics

Power calculations were performed using a detectable difference in pre-post pCO₂ of 4mmHg based on published findings (Stein & Howard, 2011). Assuming a $\beta=0.2$, a significance level $\alpha=0.05$ and $\sigma=1$, the estimated sample size needed to detect a difference is 35 subjects. To account for possible subject attrition, a total of 40 subjects will be recruited and study data will be collected at the patient's bedside using an electronic data collection form. The pre- and post- intervention capillary pCO₂ will be compared using a paired t-test and testing the null hypothesis that there is no difference in pCO₂ levels. Further analyses will test if the difference is greater than 5mmHg. In the event that distributional assumptions for the t-test are not satisfied in these data, a nonparametric Wilcoxon signed-rank test will be used to compare the pre- and post-measures. Multiple Linear Regression methods allowing for covariate adjustment will be used to determine if any significant associations exist between patient characteristics and the change in pCO₂ levels.

Planned Tables and Figures

Table 1 baseline characteristics

Figure 1 PCO₂ start vs final

Figure 2 TCO₂ vs time

Figure 3 bell shaped curve of delta pCO₂

Figure 4 Nasal Pharyngeal NAVA and RAM-cannula bell shaped curve of delta pCO₂

Table 2 characteristics of patients who failed NAVA therapy in 2 hours (if needed)

Table 3 characteristics of patients who had significant changes in pCO₂ vs those who had no changes (if needed)

Table 4 characteristics of patients who were eligible for the study but declined enrollment

References

- Maquet Critical Care AB, "NAVA and NIC NAVA in neonatal settings", pocket guide, revision 00, 2010.
- Angus, D. C., Linde-Zwirble, W. T., Clermont, G., Griffin, M. F., & Clark, R. H. (2001). Epidemiology of neonatal respiratory failure in the united states: Projections from california and new york. *American Journal of Respiratory and Critical Care Medicine*, 164(7), 1154-1160.
- Attar, M. A., & Donn, S. M. (2002). Mechanisms of ventilator-induced lung injury in premature infants. *Seminars in Neonatology : SN*, 7(5), 353-360.

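### The design sentence promises a cross-over of NAVA against CPAP or high-flow cannula, but the plan is a single-arm before-after study whose pooled test estimates the change after starting or increasing NAVA

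*Combined protocol and SAP*

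**What the plan says.** All references are to the combined protocol and SAP.

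- **Study Design:** "Prospective cross-over of NIV NAVA compared to nasal CPAP or high flow nasal cannula respiratory support". The last paragraph of the Introduction also calls the study a cross-over and describes infants "stable on their current distending pressures via continuous positive airway pressure (CPAP) or nasal cannula".
- **Study Population / Eligibility:** the modes allowed at entry are wider: "continuous positive airway pressure (CPAP), intermittent mechanical ventilation (IMV), or neutrally adjusted ventilatory assistance (NAVA"), with high-flow cannula in a further bullet. Entry needs a capillary gas within 24 hours that "demonstrates a pH of less than 7.35 and/or a partial pressure of carbon dioxide (pCO₂) greater than 45 mmHg".
- **Enrollment:** after consent, extubation and 48 stable hours, "the routinely obtained morning capillary blood gas will be monitored until the infant meets study entry criteria".
- **Baseline Data Collection:** entry mode is captured: "current mode of ventilation will be recorded four times in a one minute period".
- **NAVA settings:** "Infants who are currently receiving respiratory support via NAVA at the time of the study will have their NAVA level increased by 50" per cent, and "The other NAVA settings will be adjusted as previously described". All other infants start NAVA.
- **Study Intervention Procedure and Data Collection:** one NAVA period, measured every 30 minutes to 120 minutes, then a closing capillary gas.
- **Statistics:** one paired t-test of pre against post capillary pCO₂ (Wilcoxon signed-rank as fallback), and a regression of the change on unnamed patient characteristics.
- **Planned Tables and Figures:** the only named split of the change in pCO₂ is by interface (Figure 4).

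**The concern.** The stated comparison and the planned estimate are different quantities. A cross-over against CPAP or high flow needs each infant's outcome under both supports, in periods that can be compared. The plan provides only a value before and a value after. For infants already on NAVA, the change compares more NAVA with less NAVA. For IMV entrants, it compares NAVA with a support that the design sentence does not mention.

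What is at stake is interpretation. If the design sentence stands, a fall in the pooled mean can be reported as evidence that NAVA improves on CPAP or high flow. Part of that fall may come from infants who were on neither. All of it is open to time trend and, depending on which gas serves as the pre value, to regression to the mean.

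**Working it through.** **1. Stated design against procedures**

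| Element of a cross-over against CPAP/high flow | What the plan describes |
|---|---|
| All infants enter on CPAP or high flow | CPAP, high flow, IMV or NAVA |
| Each infant changes mode | Infants already on NAVA have the level raised |
| Comparator period with its own outcome, or a return to it | None; the study ends at 120 minutes or earlier |
| Varied order, washout, period or sequence term | None |
| Analysis contrasting the two supports | One pre-post paired test over all infants |

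**2. What the pooled test estimates.** Let S be the mean change in infants starting NAVA from CPAP or high flow, O the mean change in all other infants, and f the share of others. Then

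pooled mean = (1 − f)·S + f·O, so pooled mean − S = f·(O − S).

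If O = S, pooling changes nothing. Otherwise each 1 mmHg of difference between O and S moves the pooled mean away from S by f mmHg: 0.10, 0.25 or 0.50 mmHg at assumed shares of 10%, 25% or 50%. The documents give neither f nor the sign of O − S.

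**3. The plan's own sample size and the SD.** Stated inputs: difference 4 mmHg, σ = 1, α = 0.05, β = 0.2, n = 35. Sidedness is not stated; two-sided is assumed here. The normal formula gives (1.960 + 0.842)² × 1²/4² = 7.85/16 = 0.49, and the exact paired t-test needs 3 infants. The stated 35 is not reproduced. That is a separate matter, but it means σ = 1 cannot serve as the SD of change. Two assumed values are used instead:

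- 8.21 mmHg, the SD at which 35 infants give 80% power for 4 mmHg.
- 5.39 mmHg = 21/3.895, the pilot range (−16 to +5) over the expected range of 24 normal values.

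Both may be too large. Under a t-test, the pilot's p<0.001 at n = 24 with a mean fall of 3.5 mmHg would need an SD of at most about 4.6.

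**4. Precision of subset estimates.** 95% CI half-width = t(0.975, n−1) × SD/√n.

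| Infants | SD 5.39 | SD 8.21 |
|---|---|---|
| 35 | 2.032 × 5.39/5.916 = 1.9 | 2.8 |
| 26 | 2.060 × 5.39/5.099 = 2.2 | 3.3 |
| 18 | 2.110 × 5.39/4.243 = 2.7 | 4.1 |
| 9 | 2.306 × 5.39/3 = 4.1 | 6.3 |

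At SD 4.6 and 9 infants the half-width is 2.306 × 4.6/3 = 3.5 mmHg.

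**5. Regression to the mean.** The qualifying gas is the only capillary gas before NAVA that the plan describes, but Statistics does not say that it is the pre value. Suppose that it is, that the infant qualified on pCO₂ >45 alone, and that single gases are normal around a usual level μ with SD σ. The expected excess of the qualifying gas over μ is σ·φ(z)/(1 − Φ(z)), with z = (45 − μ)/σ.

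| Usual level μ | σ = 3 | σ = 5 |
|---|---|---|
| 45 | 2.4 | 4.0 |
| 48 | 0.9 | 2.3 |
| 50 | 0.3 | 1.4 |

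The values of μ and σ are assumptions. The mechanism is the same for every entry mode, so selecting CPAP and high-flow entrants does not remove it.

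**The case against.** **The analysis is openly pre-post.** The aim sentence in the Introduction names no comparator, the power basis is a pre-post difference, and Statistics claims no superiority. This stands. The pooled test is coherent for what it estimates; the fault lies in the design sentence and in what a reader would take from it. A loose use of cross-over for a one-way switch does not rescue that sentence, because infants already on NAVA do not switch.

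**Entry mode is not ignored.** A reader might infer that the plan cannot examine it. The documents do not support that. Mode is recorded at baseline, and Table 1, Table 3 and the regression list no variables at all, so it may well be included. The narrower statement holds: no planned analysis of the change names it.

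**Pooling need not do harm.** A reader might infer that pooling biases the result in a known direction, either by crediting CPAP/high-flow infants with an effect seen only in others or by diluting theirs. Neither is supported. The site's pilot studied infants whose NAVA support was increased and found a median change of −3.5 mmHg (p<0.001). That speaks against assuming no change in such infants, although the pilot was itself uncontrolled. Nothing is reported for infants starting NAVA from CPAP or high flow.

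**Transcutaneous CO₂ offers another baseline.** It is measured at baseline and every 30 minutes and is plotted in Figure 2. It is not the selection variable, so it is useful supporting evidence. It does not remove time trend, and the planned test uses capillary pCO₂.

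**Conclusion.** The contradiction is in the text and does not depend on any assumption: the stated comparison of NAVA with CPAP or high flow cannot be estimated from the planned data. What can be estimated is the change in pCO₂ after starting or increasing NAVA.

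The numerical effect of pooling is unknown in size and direction. It is nil if effects are equal across entry modes and small if few infants enter on NAVA or IMV.

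A reader might also infer that analysing only CPAP and high-flow entrants restores the intended comparison. It does not. Without a control period, time trend remains in every subset. Regression to the mean remains too if the qualifying gas is the pre value; under the stated assumptions it could be anywhere from 0.3 to 4.0 mmHg. The documents do not establish that it operates at that size.

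**What to change.** Reconcile Study Design, the Introduction, Eligibility, NAVA settings and Statistics:

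1. Describe the design as single-arm before-after, and the pooled test as the change in pCO₂ after starting or increasing NAVA.
2. Keep the pooled test with all infants. Add the paired change with 95% CI separately for infants starting NAVA from CPAP or high flow and for infants already on NAVA. Treat small groups, including IMV entrants, as descriptive only.
3. Make no claim that NAVA is better than CPAP or high flow. Word any statement about CPAP/high-flow entrants as a before-after change in that subset, and state the time-trend and regression-to-the-mean limitation beside it.

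The cost is wording and one table. Entry mode is already recorded, so no new data are needed and no infant leaves the main analysis. The downside is imprecision: a subset of 9 infants has a half-width of about 4 to 6 mmHg at the assumed SDs, too wide to separate no change from the plan's 4 mmHg.

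### Does the high-flow eligibility formula contradict its own PEEP of 6 and leave the PEEP under NAVA undefined?

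*Combined protocol and SAP*

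**What the plan says.** Study Population / Eligibility limits entry by birth weight ("Birth weight was less than 1500 grams with clinical history of respiratory distress syndrome treated with surfactant") and lists the permitted support modes. A separate bullet covers high flow: "Infants may be on high flow nasal cannula if the flow is large enough to provide a positive end expiratory pressure (PEEP) of 6". It equates a PEEP of 6 with 0.68 × weight (kg) + 0.92 and cites a published source. Kilograms are the only unit printed in the expression, and weight is its only variable.

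The NAVA settings section fixes the pressure for the intervention period: "Infants will be maintained on previous level of PEEP or calculated PEEP, rounding up to whole numbers". It gives no formula and does not refer back to the eligibility bullet. The same section sets the initial and back-up PIP relative to PEEP.

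Study Design makes high flow part of the comparison ("compared to nasal CPAP or high flow nasal cannula respiratory support"). Baseline Data Collection lists admission weight and current weight among the demographic data. For the ventilation data it says "and current mode of ventilation will be recorded four times in a one minute period". During the intervention, the Safety section adds: "Current NAVA settings, oxygen saturations, FiO₂, and blood pressure (BP) will also be recorded at these times".

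**The concern.** Taken at face value, the formula is false for every infant in the trial. It calls something a PEEP of 6 and equates it with an expression that stays below 2 for any weight under 1.5 kg. It has no flow term, although the criterion is about flow.

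The doubt carries into the NAVA settings section. The eligibility expression is the only PEEP formula in the document, so a reader looking for the calculated PEEP may take it to be that. Used as a pressure and rounded up, it would give a value far from the 6 in the eligibility bullet, and the PIP settings would move with it.

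The stake is the main comparison, which is paired pre- and post-intervention capillary pCO₂ (Statistics). If PEEP changed when a high-flow infant moved to NAVA, the effect of that change would be mixed with the effect of NAVA. The listed baseline fields include mode but not the pre-switch flow or set PEEP, so the listed data alone would not show such a change.

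**Working it through.** **Inputs.** From Study Population / Eligibility: slope 0.68 per kg, intercept 0.92, stated PEEP 6, birth weight below 1.5 kg. Write f(w) = 0.68w + 0.92.

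**Literal reading: f is a pressure.**

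| Weight (kg) | f(w) | Rounded up |
|---|---|---|
| 0.5 | 0.34 + 0.92 = 1.26 | 2 |
| 1.0 | 0.68 + 0.92 = 1.60 | 2 |
| 1.5 | 1.02 + 0.92 = 1.94 | 2 |
| 4.0 | 2.72 + 0.92 = 3.64 | 4 |

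Solving f(w) = 6 gives w = (6 − 0.92)/0.68 = 7.47 kg. The 1.5 kg limit applies at birth and current weight may be higher, but even an assumed 4 kg gives only 3.64. The stated 6 is not reproduced at any plausible weight.

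**What that reading implies.** Flow would play no part in a criterion that asks whether flow is large enough. No infant in the population would reach 6, so a bullet written to admit high-flow infants would admit none. Study Design names high flow as a comparator. A reading that empties the bullet and conflicts with the design is not the one to adopt.

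**Flow reading: f is the flow that gives a PEEP of 6.** The left side is then a label for that flow. The result varies with weight (1.60 at 1.0 kg, 1.94 at 1.5 kg), which suits a threshold an infant's flow must meet. A flow of 1.94 and a pressure of 6 are different quantities, so there is no discrepancy between them, and the 7.47 kg solution has no meaning. The unit of flow is not printed. The weight is not specified either; for an infant assessed at entry, current weight is the ordinary meaning, and it is recorded. The choice moves the threshold by 0.68 per kg of difference, for example 1.94 − 1.60 = 0.34 between 1.0 and 1.5 kg.

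**The two sections side by side.** The NAVA settings sentence says infants are maintained on a PEEP, so its stated aim is continuity. The previous level covers infants who already have a set PEEP. The calculated PEEP is needed only where there is none, presumably on high flow. Three readings are open:

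1. f as a pressure. This rounds up to 2 for weights up to (2 − 0.92)/0.68 = 1.588 kg and conflicts with the 6 in the eligibility bullet.
2. f as a flow threshold only. This returns no PEEP for an infant whose flow is above the threshold.
3. Each admitted high-flow infant is taken to have the PEEP named in the criterion. The two sections then agree.

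The text does not say which is meant, and the clinical team must supply the value. For the statistical point it is enough that a consistent reading exists and that the conflicting one depends on the literal reading rejected above.

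**Effect on the result.** Shift in mean pCO₂ change = share of infants on high flow × mean pCO₂ effect of any PEEP change at the switch. The documents give neither factor. If PEEP does not change, the shift is zero. The Statistics section's benchmark ("Power calculations were performed using a detectable difference in pre-post pCO₂ of 4mmHg") gives a scale of 4 mmHg, but there is nothing in the documents to set against it.

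**The case for a change.** The strongest case for a change is that a protocol should not need its reader to replace the left side of an equation, and that a literature citation does not make the criterion self-contained. The missing unit, the unspecified weight and the undefined calculated PEEP are real omissions. The instruction to round up adds some doubt, because a fixed 6 needs no rounding, although a non-integer previous PEEP would explain it. The ambiguity also reaches other settings. Initial PIP is at least 8 cm H₂O above PEEP and back-up PIP is 12 above it. A PEEP of 2 would imply at least 10, and 14; a PEEP of 6 would imply at least 14, and 18. An infant whose flow was above the threshold might also not stay at the previous pressure.

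These points stand as comments on clarity. They do not show an arithmetic error, a wrong pressure in use, or a biased comparison. The protocol requires a physician from the research team at the bedside for the whole intervention, so someone able to settle the setting is present for each infant. Mode is recorded at baseline and NAVA settings during the intervention. PEEP appears under the NAVA settings heading and so is plausibly captured.

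Adding flow and set PEEP to the baseline fields, and reporting pCO₂ change by baseline mode, would correct no wrong result. The electronic data form is not shown and may already hold the first. For the second, 40 infants over four permitted modes average 40/4 = 10 per mode, which is thin. The Statistics section already plans regression of pCO₂ change on patient characteristics, although it does not name mode.

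**Conclusion.** The concern does not call for a change. The gap between 1.94 and 6 comes from comparing a flow with a pressure and is not an error in the plan's figures. What is left is loose notation and a missing cross-reference, confined to infants without a set PEEP. Clinical staff at the bedside can be expected to fill that gap sensibly.

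The size of any effect on the pCO₂ comparison cannot be derived from the documents, and it is zero if the switch leaves PEEP unchanged. The conclusion rests on two assumptions. The first is that the expression is a flow threshold, as the wording of the criterion implies but does not state. The second is that the calculated PEEP applies only to infants without a previous set level. It takes no position on which pressure is clinically correct.

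### The main paired test does not define its pre-intervention capillary pCO₂; if it is the qualifying gas, as the procedures imply, the test includes regression to the mean of unknown size in NAVA's favour

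*Combined protocol and SAP*

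**What the plan says.** All references are to the combined protocol and SAP.

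- **Statistics.** The main analysis is a paired t-test of pre- against post-intervention capillary pCO₂, with a Wilcoxon signed-rank fallback, a further test against 5 mmHg, and a regression on the change. The pre value is not defined. Nor is the starting PCO₂ in Figure 1 (Planned Tables and Figures).
- **Study Population / Eligibility.** Entry needs a capillary gas "within 24 hours of study entry that demonstrates a pH of less than 7.35 and/or a partial pressure of carbon dioxide" above 45 mmHg. The infant must also be "At least 48 hours post-extubation and medically stable as determined by the treating medical team".
- **Enrollment.** After consent, "the routinely obtained morning capillary blood gas will be monitored until the infant meets study entry criteria".
- **Baseline Data Collection.** Vital signs, TCO₂ "and current mode of ventilation will be recorded four times in a one minute period and the values averaged to minimize normal variation". No capillary gas is listed.
- **Study Intervention Procedure and Data Collection.** Under this heading, "At initiation of intervention, and at time 30, 60, 90, and 120 minutes, TCO₂, heart rate (HR), respiratory rate (RR") and ventilator variables are recorded. Again no capillary gas is listed at the start. One is drawn at completion or early exit.
- **Study Design.** "Prospective cross-over of NIV NAVA compared to nasal CPAP or high flow nasal cannula respiratory support in VLBW infants". No comparator period with its own start and end gases is described.

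**The concern.** A value followed day by day until it crosses a limit is, on average, an upward excursion for that infant. If the infant's usual pCO₂ is steady, the next gas tends to be lower without any treatment. Using the qualifying gas as the pre value puts that fall into the t-test, the Wilcoxon fallback, the 5 mmHg test and the regression on change. The direction favours NAVA. A true cross-over would let a comparator period absorb it, but none is described. At stake is whether a significant fall in capillary pCO₂ can be credited to NAVA.

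**Working it through.** **1. The plan's own figure.** Statistics gives 35 infants for a 4 mmHg difference with σ = 1, α = 0.05 and β = 0.2. A paired t-test with those inputs needs 3. A result of 35 needs an SD of change of about 8.2 mmHg (t) or 8.4 (normal: 4 × √35 / 2.80). That mismatch is a separate matter. It is used here only as one indication of the SD of change the design may have had in mind.

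**2. A second indication of that SD.** In Preliminary Data, "the differences ranged from a decrease of 16 mmHg to an increase of 5 mmHg" in 24 infants, a range of 16 + 5 = 21 mmHg. The expected range of 24 normal values is about 3.9 SDs, so the SD of change is about 21 / 3.9 = 5.4 mmHg.

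**3. Model.** Each infant has a usual pCO₂ drawn from N(m, s_b). Each gas adds an error with SD s_w, and the correlation between gases *g* hours apart is ρ(g) = 0.5^(g/24). The pre value is the first of up to five morning gases to meet either limb of the entry rule. NAVA has zero mean effect. Then:

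- expected change = −(1 − ρ(g)) × E, where E is the mean error of the qualifying gas;
- SD of change ≈ s_w × √(2(1 − ρ(g))), before any variation in individual response.

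Assumed inputs: s_b = 5; s_w = 3.8 (5.4 / √2); m = 45, 50 or 55; pH = 7.40 − 0.008 × (pCO₂ − 40), plus an infant SD of 0.04 and noise SD of 0.01. None of these stands in the documents except the 5.4, which is derived from the pilot range.

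**4. Size of the fall.** At m = 45 and a 24-hour gap, simulation gives a fall of 0.89 mmHg, so E = 0.89 / 0.5 = 1.78. At 4 hours, ρ = 0.5^(4/24) = 0.891 and the fall is 0.109 × 1.78 = 0.19 mmHg. At 24 hours the fall is about 0.4 mmHg at m = 50 and 0.1 at m = 55.

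**5. False-decrease rate, n = 35, nominal 2.5%.** Approximately P(Z < −2.03 + fall × √35 / SD). At m = 45, 24 hours and SD 5.4: 0.89 × 5.92 / 5.4 = 0.98, and P(Z < −1.05) ≈ 15%. Simulated results with the SD of change raised to 5.4 by varying individual responses:

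| Usual mean | Gap 24 h | Gap 8 h | Gap 4 h |
|---|---|---|---|
| 45 | 15% | 6% | 4% |
| 50 | 6% | 3.5% | 3% |
| 55 | 3% | 3% | 3% |

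**6. Sensitivity at m = 45, 24-hour gap.**

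- SD of change near 8: about 9%.
- No variation in response (SD of change 3.7): 28%.
- Independent errors: fall about 2.1 mmHg, about 65%.
- s_w = 5.4: fall 1.4 mmHg, about 35%. The division by √2 in step 3 assumes independent errors. At correlation 0.5, √(2 × 0.5) = 1, so the pilot SD would give s_w = 5.4. The 3.8 is therefore not an upper bound.

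No rate is given for the 5 mmHg test, because the plan states neither its α nor its sidedness.

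**The case against.** - **Another start gas may exist.** The measurement lists need not be exhaustive. A separate gas drawn just before NAVA would largely remove the bias. This stands, and is why the point is conditional: a reader might infer that the analysis certainly uses the qualifying gas, but the documents do not say so.
- **The direction is also conditional.** Medical stability is the treating team's judgement and does not establish a steady pCO₂. An infant whose pCO₂ was drifting up could show less fall, or none. An infant who enters on pH alone carries weaker selection on pCO₂.
- **The size may be small.** With correlation 0.5 and an SD of change of 5.4, the excess is material only when the usual mean is near 45 and the gap is near 24 hours. The documents establish neither.
- **Stronger readings are tempting.** A reader might infer that the error rate is 28% or 65%, or that regression to the mean could account for the whole 4 mmHg. The 28% needs an SD of change of 3.7, below both values derived from the documents (5.4 and 8.2). The 65% needs independent errors and a mean of 45. The fall of 0.89 mmHg is 0.89 / 4 = 22% of the design difference. Nor do the documents show that two analysts would pick different gases, since only one candidate is described.
- **Naming the qualifying gas does not repair the test.** Correct: its error rate is unchanged. The gain comes from limiting what that test may conclude and from adding a second comparison.

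**Conclusion.** The gap in the text is certain: the pre value of the main test is undefined, and the only one the procedures supply was selected for crossing a limit. On that reading, and for infants with a steady usual pCO₂, the bias runs towards a NAVA benefit. Its size cannot be learned from the documents, which give no usual mean, within-infant SD, correlation or gap between gases. Under the assumed inputs it runs from negligible to a clear excess of false decreases, and neither the 15% nor the 65% is an estimate for this trial. I rate it as should-fix: the definition and the limit on interpretation are needed, but the documents do not show that the main test is badly wrong.

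**What to change.** 1. Name one pre gas for every infant in the SAP, and use the same definition for Figure 1.
2. If it is the qualifying gas, state that the capillary change includes regression to the mean, that this definition does not remove it, and that the fall will not be attributed to NAVA from the capillary test alone.
3. Prespecify, with an estimate and 95% CI, a paired comparison of the four-reading baseline TCO₂ (current mode, before NAVA is started or increased) with the four-reading TCO₂ at 120 minutes. At present TCO₂ appears only in Figure 2. For infants who stop early, record a four-reading TCO₂ at stopping, with the last scheduled reading as a sensitivity analysis.
4. If a capillary gas not used for eligibility is routinely available just before NAVA, prespecify an analysis with it as the pre value.

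**Cost.** SAP wording and one recorded item at early exit, from a monitor already running. No extra heel stick, and the capillary endpoint and its N are unchanged.

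**Limits.** TCO₂ is indirect, and N was not set for it: at n = 35 the CI half-width is 2.03 × SD / √35, or 1.0, 1.7 or 2.7 mmHg for an assumed SD of change of 3, 5 or 8. It also drives titration ("At 60 minutes of intervention if the TCO₂ average has not decreased by 5 mmHg from baseline or has risen", and again at 90 minutes) and early exit, so exit readings are themselves selected. A small bias remains if NAVA starts soon after the qualifying gas. With E = 1.78 and a start at 2 hours it is 1.78 × (0.944 − 0.891) = 0.09 mmHg, against 0.19 for the capillary change; with a start at 22 hours it is 1.78 × (0.530 − 0.500) = 0.05, against 0.89. It would be larger if errors fade within hours. The comparison does not replace a control period.
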